APPENDIX D: PATIENT STUDY DIARY

Today's date _____

Agent: CB-5339 Dose: _____

Patient Name _____ (*initials acceptable*)

Patient Study ID _____

INSTRUCTIONS TO THE PATIENT:

1. Complete one form for each cycle (28 days, or 4 weeks) of treatment.
2. You will take _____ capsules (____ mg per capsule) of CB-5339 once daily on days 1-4 each week for each cycle. Take your dose at approximately the same time each day. CB-5339 should be taken with water only on an empty stomach (that is, at least 1 hour before or 2 hours after a meal).
3. Record the date and times when you took CB-5339.
4. If you miss or vomit the dose within 6 hours, please make a note of this in the Comments column and do not make up the dose.
5. If you have any comments or notice any side effects, please record them in the Comments column. **If you have any changes in vision, please call the study team immediately.**
6. Please bring this form and any unused CB-5339 when you return for each appointment.

[figure not shown]
Day	Date	Time of CB-5339 dose	Dose Taken	Comments
1	Week 1			
2				
3				
4				
5	Do not take CB-5339 today			
6	Do not take CB-5339 today			
7	Do not take CB-5339 today			
8	Week 2			
9				
10				
11				
12	Do not take CB-5339 today			
13	Do not take CB-5339 today			
14	Do not take CB-5339 today			

15	Week 3			
16				
17				
18				
19	Do not take CB-5339 today			
20	Do not take CB-5339 today			
21	Do not take CB-5339 today			
22	Week 4			
23				
24				
25				
26	Do not take CB-5339 today			
27	Do not take CB-5339 today			
28	Do not take CB-5339 today			

Patient's signature: _____

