5. TREATMENT PLAN

This is a first-in-human, open-label phase 1 trial of oral CB-5339 in adult patients with advanced metastatic solid tumors and lymphoid malignancies. The study will be conducted in two parts, an initial dose-escalation phase followed by a dose expansion phase at the recommended phase 2 dose (RP2D) in the same patient population. Additional expansion cohorts may be considered to explore pharmacodynamic endpoints at lower dose levels (a protocol amendment will be submitted for these changes to the trial design).

Patients will be required to maintain a study diary documenting when the doses were taken, and any associated side effects ([Appendix D](#)). Patients will be asked to return the diary to the clinic staff at the end of each cycle.

Patient evaluations will be performed throughout the study as described below. Baseline history, physical examination, laboratory evaluations, and ECG must be conducted within 8 days prior to start of protocol therapy. If protocol therapy is started within 8 days of the eligibility screening evaluations (see [Section 3.4](#)), the results from these screening evaluations may be used as baseline measurements. If > 8 days have passed since the screening evaluations, the medical history, physical examination, laboratory evaluations, and ECG must be repeated prior to starting protocol therapy.

Baseline tumor imaging must be performed within 28 days prior to start of protocol therapy. If protocol therapy is started within 28 days of the eligibility screening tumor imaging, the screening evaluation imaging results may be used as baseline measurements; if > 28 days have passed since the screening evaluation tumor imaging, the imaging must be repeated prior to starting protocol therapy.

History and physical examination will be performed at baseline (within 8 days of the start of protocol therapy), during weeks 1, 2, 3, and 4 of cycle 1, and at the start of every cycle thereafter (within 3 days prior to treatment). Physical examinations will include O₂ saturation measured by pulse oximeter.

The first three patients on study will be admitted to the NIH Clinical Center for 5 days of in-patient evaluation followed by out-patient evaluation at the day hospital on days 6 and 7 (vital check, PO₂, serum chemistries, and CBC).

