Labs (CBC with differential; serum chemistries) will be performed at baseline (within 8 days of the start of protocol therapy), during weeks 1, 2, 3, and 4 of cycle 1, and at the start (+/- 1 day during the cycle and up to 3 days before start of a new cycle) and during week 1 of every cycle thereafter. For the first three patients enrolled on the study who will receive their initial week of treatment as inpatients, labs will also be performed on Cycle 1 Day 2 prior to CB-5339, on Day 3 based on the result from Day 2, on Day 4 prior to CB-5339, on Day 6 (Sunday at the Day Hospital), and on Day 8 (C1W2).

ECG will be performed at baseline (within 8 days of the start of protocol therapy) and will be

performed on day 1 pre-dose and at 2 hours post dose/the time to peak concentration of every subsequent cycle, and as clinically indicated.

Blood and urine samples for correlative PD and PK studies will be collected from all patients as described in [Section 7](#).

Paired tumor biopsies will be collected at baseline and then 4-6 hours after receiving the first dose in the expansion cohort; an optional biopsy may be collected at disease progression or “pre-progression” (defined as a 10-19% increase in tumor volume as shown on a restaging scan).

NEI associate investigators will perform an ophthalmology examination that includes optical coherence tomography (OCT), color vision testing, and a questionnaire on all patients during screening. The questionnaire will be repeated after treatment on cycle 1 day 1 or 2; the questionnaire and eye examinations can be repeated by NEI as clinically indicated. Details about the questionnaire and eye examinations can be found in [Appendix B](#) along with thresholds for pre-existing visual impairment. Patients should be encouraged to report any vision changes to the study team immediately.

CB-5339 is administered orally on a schedule of once daily, 4 days on and 3 days off (28-day cycle). Dose escalation will continue until the RP2D (MTD) is established. Intra-patient dose escalation will be permitted; refer to Section 5.2 regarding conditions for permitted intra-patient dose escalation.

Dose Escalation Schedule	
Dose level	Dose of CB-5339 (mg/day, once daily 4 days on/3 days off weekly)
-1	25 mg/day; 3 days on/4 days off
1 (starting)	25
2	50
3	100
4	150
5	225
6	300

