5.5 Duration of Therapy

In the absence of treatment delays due to adverse event(s), treatment may continue until one of the following criteria applies:

- Disease progression
- Intercurrent illness that prevents further administration of treatment
- Significant toxicity occurs despite 2 dose reductions or no lower dose level exists,
- Patient decides to withdraw from the study
- General or specific changes in the patient's condition render the patient unacceptable for further treatment in the judgment of the investigator
- Patient non-compliance
- Pregnancy
- Termination of the study by sponsor
- The drug manufacturer can no longer provide the study agent

The reason(s) for protocol therapy discontinuation, the reason(s) for study removal, and the corresponding dates must be documented in the Case Report Form (CRF).

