5.8 Dosing delays

Doses of CB-5339 will be held or modified only for adverse events that are felt to be at least possibly related to study drug. Treatment may be delayed for a maximum of 2 weeks for resolution of toxicities; in case toxicities do not resolve as defined below, the patient will not receive further therapy on this protocol and will be followed for resolution of toxicities. Dose modifications are intended for within-cycle and start of next cycle changes. If administration of CB-5339 is interrupted for any reason, it will not be made up, and counting of the cycle days will continue.

Patients will be allowed up to 2 dose reductions. For patients on dose level 1, the dose will be reduced to dose level -1 (25 mg/day; 3 days on/4 days off each week q 28-day cycles). Patients

who require a dose reduction will not have the dose re-escalated.

Treatment may be delayed for a maximum of 1 day during a cycle due to unavoidable scheduling conflicts.

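### The only patient diary prints four dosing days a week, so a patient on dose level -1 (three days a week) is told in print to take the unreduced level 1 schedule

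*Combined protocol and SAP*

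**What the plan says.** The dose escalation table in Section 5 (also in the Schema) defines level -1 as "25 mg/day; 3 days on/4 days off". Level 1 is the same 25 mg a day on the standard four-on, three-off week. Section 2.2.6 states the purpose: level -1 lowers the frequency of administration by 25%. Section 5.8 makes it the reduction step for patients at level 1: "the dose will be reduced to dose level -1 (25 mg/day; 3 days on/4 days off each week". It also makes any reduction permanent, since patients "who require a dose reduction will not have the dose re-escalated".

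Section 5 requires patients to keep the Appendix D diary, the only diary listed in the table of contents. Its second instruction reads "of CB-5339 once daily on days 1-4 each week for each cycle". In the day grid, the no-dose notice is printed only on days 5-7, 12-14, 19-21 and 26-28; days 4, 11, 18 and 25 are open for a dose. The daily dose, number of capsules and capsule strength are blanks. The dosing days are not.

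On checks, Section 5 says: "Patients will be asked to return the diary to the clinic staff at the end of each cycle". The diary itself tells patients to bring it, with unused capsules, to each appointment. Physical examinations take place "during weeks 1, 2, 3, and 4 of cycle 1, and at the start of every cycle thereafter". After cycle 1, laboratory tests fall at the start and in week 1 of each cycle.

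**The concern.** The diary is the written dosing instruction the patient takes home, and for level -1 it contradicts the protocol. Completing every blank correctly does not help, because level -1 changes the one item that cannot be filled in. The capsule gives no signal either: it is the same 25 mg once a day.

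Two groups could be affected if the form is issued unaltered and followed.

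- **Patients reduced for toxicity.** They are meant to receive less drug and would continue on the schedule that preceded the toxicity. If toxicity persists, Section 5.5 ends treatment when "Significant toxicity occurs despite 2 dose reductions or no lower dose level exists". A patient could be judged to have failed level -1 without having received it.
- **A cohort enrolled at level -1.** Two dose-limiting toxicities (DLTs) there put the study on hold (Section 5.2). If the error ran through cycle 1, those events would have arisen on the level 1 regimen and would say nothing about level -1.

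**Working it through.** **Inputs.** 25 mg per dose at levels 1 and -1; four dosing days a week at level 1 and three at level -1 (Sections 5 and 5.8); four weeks per cycle; four printed dosing days a week (Appendix D).

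**The plan's own figure.**
- Level 1: 4 × 4 = 16 doses; 16 × 25 = 400 mg per cycle.
- Level -1: 3 × 4 = 12 doses; 12 × 25 = 300 mg per cycle.
- Reduction: 1 − 12/16 = 25%, which agrees with Section 2.2.6.

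**Effect of following the diary.** Let w be the number of weeks in a cycle in which the patient takes the printed fourth dose. Doses = 12 + w. Remaining reduction = 1 − (12 + w)/16. Excess over the prescribed level -1 regimen = w/12.

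| Weeks with a fourth dose | Doses | mg per cycle | Reduction vs level 1 | Excess vs level -1 |
|---|---|---|---|---|
| 0 | 12 | 300 | 25% | 0% |
| 1 | 13 | 325 | 18.75% | 8.3% |
| 2 | 14 | 350 | 12.5% | 16.7% |
| 3 | 15 | 375 | 6.25% | 25% |
| 4 | 16 | 400 | 0% | 33.3% |

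**Who can reach level -1.** Section 5.8 allows two reductions.
- From level 1: 1 → -1, one step.
- From level 2: 2 → 1 → -1, two steps.
- From level 3: 3 → 2 → 1 uses both steps and stops short of -1.

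Besides these patients, a cohort enrolled at level -1 would have 3 to 6 patients under the 3+3 rules. In the accelerated phase only one patient starts at each of levels 1 and 2. Expansion patients are exposed only if the recommended phase 2 dose is 25 or 50 mg a day.

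**Whether the existing checks would catch it.**
- In cycle 1, weekly visits with the diary in hand could stop the error after one extra dose.
- From cycle 2, a week 1 contact on or after day 4 could show the extra dose, but one before day 4 could not. With no other appointment, the next diary review is at the end of the cycle, so up to four extra doses are possible when the reduction takes effect on day 1.
- The compliance measure in Section 5.1 is a minimum of 90% of prescribed doses, applied after cycle 2. Taking 16 doses when 12 are prescribed passes it.
- Section 6.1 supplies 30-capsule bottles and recommends dispensing in the original container, so 16 single-capsule doses do not exhaust the supply.
- Section 5.8 allows reductions within a cycle, while the diary is one form per cycle. Nothing tells staff to replace the form the patient already holds.

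**The case against.** The governing text is clear: every protocol statement of level -1 says three days on, four off, and the diary matches levels 1 to 6. No dosing rule, endpoint or decision rule is wrong; one template omits a contingency level. Harm needs several things together: level -1 is used, staff issue the form unaltered, the patient follows the print over any verbal advice, and the visits miss it. The diary records the date and time of each dose, so a review would expose the error before anyone concluded that level -1 had failed. For a level -1 cohort, the four weekly visits, the investigator's sign-off on dose decisions and the at least monthly calls with the CTEP medical officers (Section 12.1) all stand in the way. Four extra doses is a ceiling: a mid-cycle reduction leaves fewer dosing weeks, and additional monitoring is allowed. At worst the patient stays on the protocol's own starting regimen.

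Much of this stands. The reach is small, the harm is bounded, and the consequences for treatment discontinuation and the DLT count are conditional; the cohort consequence is the less likely of the two. The objection does not remove the contradiction. No section tells staff to correct or replace the form, and the safeguards work only after at least one unintended dose. The people exposed are those for whom the protocol has already decided that less drug is needed.

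**Conclusion.** The concern holds. As printed, Appendix D gives a level -1 patient the level 1 schedule. Followed for a full cycle, it means 16 doses (400 mg) instead of 12 (300 mg): 33% more than prescribed, with the intended 25% reduction wholly lost. Caught after one week, it means 13 doses (325 mg) and a reduction of 18.75%.

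These figures assume the form is issued uncorrected and followed, with the reduction in force from day 1 of a cycle. The documents give no basis for putting a probability on that. Exposure cannot exceed level 1, and the number of patients affected may be zero. That there is no second diary rests on the table of contents and the appendices available for review. The point should be fixed because a patient-held instruction contradicts a toxicity reduction in a first-in-human trial and the correction costs almost nothing.

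**What to change.** Either of two changes to Appendix D is enough:

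1. Add a level -1 version with three dosing days and four no-dose days each week, for example doses on days 1-3, 8-10, 15-17 and 22-24. The sponsor should confirm which three days are intended.
2. Make the dosing days a field completed for each patient, in the instruction and in the day grid, as dose, capsule count and strength already are.

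In addition, state in Section 5.8 that the diary is replaced whenever the dose level changes, including within a cycle.

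With either change, level -1 stays at 12 doses (300 mg) per cycle and keeps the 25% reduction. The cost is one diary page or one fillable field, plus one sentence. No patients, visits or procedures are added.

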APPENDIX E: SOP FOR PBMC PREPARATION (PD)

1. Whole blood collected in green-top (sodium heparin, BD Diagnostics, Cat# 367878, size 13x100mm) collection tubes (5-6 mL/tube).
2. Depending on total blood collection (5-15 mL from 1-3 tubes), prepare separate 50mL PBMC separation tubes. Each separation tube can hold a maximum of 7.5 mL of blood (if >7.5 mL blood, prepare two tubes). Bring Ficoll (Ficoll-Paque PLUS< GE Healthcare, Cat# 17144002) to room temperature. Add 10 mL Ficoll to each 50-mL tube.
3. If total amount of blood is >7.5 mL, pool whole blood from 2-3 green-top (sodium heparin) collection tubes into one 50 mL tube.
4. Dilute pooled whole blood 1:1 (one-part blood one-part PBS) with 1x PBS (from step-3), close the tube and mix slowly by inverting tube.
5. Carefully overlay 15 mL of diluted blood+PBS mixture on top of the Ficoll layer using a 25 mL pipettor set on the lowest speed to avoid mixing the blood and Ficoll. This step is critical for the purity of PBMCs. To avoid mixing blood and Ficoll, the tube should be held at an angle and the blood mixture released very slowly. It is important to not layer >15 mL because it may decrease the total PBMC yield/mL of blood.
6. Centrifuge 50 mL tubes (from step-5) at 800xG for 30min at room temperature in a swing-out rotor. Importantly, **the rotor breaks must be inactivated to prevent mixing of phases**. Equally important is any changes in temperature (use of pre-cooled centrifuge) can change the density ratios and have an impact on the separation quality.
7. The PBMCs will be in the cloudy middle buffy layer (sometimes not clearly differentiated). Collect PBMCs by carefully inserting a 5 mL pipette and collecting all buffy layer, which varies in content. Transfer buffy layer to a new labeled 50 mL tube, a little excess (1-2 mL) to capture all buffy layer is acceptable. Each buffy layer should be collected in a separate tube to allow for adequate dilution of Ficoll. Dilute contents with 1x PBS to a total volume of 50 mL (min 5x buffy layer volume – 50 mL total).

8. Centrifuge tubes from step-7 at 300xG for 7 min at room temperature.

9. There should be a visible cell pellet at the bottom of the tube. Carefully aspirate supernatant (without touching the cell pellet) from each 50 mL tube and discard. Resuspend the cell pellet in 1.5 mL 1x PBS. If more than one tube is processed per patient, then combine suspended cells into one 50 mL tube. For two tubes there will be a total of 3 mL cell suspension.

10. For counting, prepare a 1:10 dilution of sample using PBS (20 μ L sample + 180 μ L 1x PBS).

11. Refer to the SOP Appendix-3 (next page) for cell counting. Cells can also be counted using AO/PI stain (Necelon, Cat# CS2-0106-5mL); mix 20 μ L of 1:10 sample dilution with 20 μ L of dye (1:2 dilution), count using Cellometer, record counts for calculation of total number of cells.

[figure not shown]
12. Centrifuge tubes from step-9 at 500xG for 5 min at room temperature, aspirate supernatant and discard. Resuspend cell pellet in 1 mL of ice cold 1X PBS and transfer (split cells) to only two 1.5 mL microcentrifuge tubes.

13. Centrifuge the samples at 10,000g for 5 minutes at 4°C, carefully completely remove supernatant (residual PBS interferes with cell extraction) and snap-freeze on dry ice.

DCTD Standard Operating Procedure (SOP)

Title:	PBMC Specimen Collection, Preparation, and Freezing for Protein Extraction			Page 18 of 19
Doc. #:	SOP340503	Revision:	H	Effective Date: 2/11/2015

APPENDIX 3: HEMOCYTOMETER CELL COUNT

1. Prepare hemocytometer chamber and cover glass for use by cleaning with 70% ethanol and wiping dry with Kimwipes.
2. Place cover glass squarely on top of hemocytometer and transfer 10 to 20 μL of a 1:5 trypan blue stained dilution of cells (20 μL sample + 60 μL 1X PBS + 20 μL 0.4% trypan blue) under cover glass on one side of hemocytometer and allow cells to settle.
3. Using the 20X objective, locate the upper left square of one grid (A).
4. When counting cells follow these general guidelines:
 - a. The middle of the triple lines separating each corner square (A-D) is the boundary line. Cells that touch the upper or left boundaries are included, but cells that touch the lower or right boundaries are excluded.
 - b. Optimal cell counts should be 30-150 cells/corner area, do additional 1:5 dilutions for high density specimens
 - c. If greater than 10% of particles are clusters of cells, try to disperse cells in original trypan blue suspension and repeat the count.
5. Count total cells (white and blue cells) in each corner area (A - D) of the hemocytometer using a snake-like motion as indicated in corner B. Record all 4 counts (A, B, C, and D) in the Batch Record.
6. Count viable cells (white cells only) in the same manner. Record all 4 counts (A, B, C, and D) in the Batch Record.
7. Total cells and total viable cells/mL can be determined using the following equation:

$$\text{Cells/mL} = \left(\frac{\text{Total Cells A+B+C+D}}{4} * 10,000 \right) * \text{dilution factor}$$

